2.2.2. Secondary Outcome

The feasibility of undertaking a study with this group of elderly, vulnerable people in a care home setting including assessing the feasibility of the outcome of the future trial such as quality of life outcome.

3. Study Design

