3.1. Study Description

An observational case-controlled study with three groups of participants with 1:1:1 will be carried out. A total of 60 volunteers, 20 in each group from the following groups (i) Alzheimer's dementia and challenging behavioural symptoms, (ii) Alzheimer's dementia and no challenging behavioural symptoms, (iii) without any type of dementia, will be recruited from care homes.

Each volunteer (assisted by staff) will provide two faecal samples, at least a week apart which will be analysed for microbial composition and activity by assessing Short Chain Fatty Acid profile (SCFA profile). Faecal samples will be collected using a pot on a toilet/commode, which will be sealed and processed in the laboratory within 12hr.

Additional information on regular diet composition will be collected by accessing the weekly care home menu. Staff will observe participants and record every episode which requires staff intervention as a result of behaviours that are challenging to manage.

A quality of life questionnaire will be completed by each volunteer in Alzheimer's dementia groups using DEMQOL (Dementia Quality of Life questionnaire).

DEMQOL is widely used patient reported outcome measures (PROMs) of health related quality of life in people with dementia.

Finally, we will collect other information on medication, personal characteristics, co-morbidities etc. to mitigate any confounding effects.

To achieve the secondary objectives the following outcomes will be assessed.

We will collect information on the following key aspects of feasibility of a larger study (future clinical trial) based on the main hypothesis driven work carried out under aim 3 described below

- (1) Proportion of eligible older people with Alzheimer's dementia with or without challenging behaviours
- (2) Proportion of eligible participants willing to participate
- (3) Proportion of participants who are able provide samples in each group
- (4) Proportion of participants (staff who are looking after them or relatives) who are able to provide study data /information

We will assess participants, their carers and whenever relevant managers and staff of care home and relatives/family members and people with Alzheimer's dementia with regard to willingness to participate in a research trial and to identify issues to be addressed to gain support for such an intervention trial through end of study questionnaire conducted by the study research nurse face to face.

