This will explore the practical issues which need to be considered in the future study. A study completion questionnaire will be introduced after sampling is complete (Appendix B).

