5.4. Ineligible and Non-Recruited Participants

Only eligible volunteers will be recruited to the study, up to the required number in each group. Once this number is reached, any additional interested volunteers will be thanked for their interest. No data will be collected prior to recruitment.

6. Withdrawal Procedures

If any participant wishes to withdraw from the study at any point after recruitment, all data and samples collected will be destroyed. If the carer perceives that participation in the study is causing distress to the volunteer, they will provide advice but if the distress persists the volunteer may be withdrawn from the study. In both cases a 'withdrawn from study' form will be completed and attached to the CRF. Unless such a form is completed (by either the volunteer or their representative) and consent is thus withdrawn, all samples will be kept following appropriate study guidelines. As the study requires 20 participant in each arm of the study, we will replace the withdrawal with further recruitment.

7. Data Collection and Management

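### Withdrawers' data are destroyed and withdrawers replaced, while feasibility proportions (3) and (4) have no defined denominator, so those figures may rest on the retained 20 per group alone

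*Combined protocol and SAP*

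**What the plan says.** Four parts of the protocol bear on this.

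- **The outcome.** Section 2.2.2 makes feasibility the secondary outcome: "The feasibility of undertaking a study with this group of elderly, vulnerable people in a care home setting". Section 3.1 lists four measures, two of which arise after consent: (3) "Proportion of participants who are able provide samples in each group" and (4) "Proportion of participants (staff who are looking after them or relatives) who are able to provide study data /information". Section 9.3 adds that collecting two samples per person is itself a test of the collection process for the main study.
- **The withdrawal rule.** Section 6 says: "If any participant wishes to withdraw from the study at any point after recruitment, all data and samples collected will be destroyed". It then says: "As the study requires 20 participant in each arm of the study, we will replace the withdrawal with further recruitment".
- **The withdrawal record.** Section 6 covers two situations, a participant's wish to leave and distress perceived by the carer. It says: "In both cases a 'withdrawn from study' form will be completed and attached to the CRF". The next sentence keeps samples unless such a form has been completed and consent thereby withdrawn.
- **The analysis.** Section 9.2 plans descriptive analysis for the secondary objectives. Section 9.3 deals with missing time points. Neither gives a denominator or analysis set for (3) and (4), and neither mentions withdrawals or replacements.

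**The concern.** A person who consents and then leaves because sampling proved distressing or impractical is a failure that a feasibility study needs to count. Under Section 6 that person's data are destroyed and someone else takes the place. If (3) and (4) are then calculated on the 20 people present in each group at the end, the leaver appears in neither numerator nor denominator.

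At stake is how far the feasibility figures can be relied on. The summary and Section 9.4 say that the results will support a further grant application. A future trial planned on optimistic figures would recruit too few people. Destruction cannot be undone, so the loss cannot be repaired at the analysis stage.

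**Working it through.** **Inputs from the documents.** Section 3.1: "A total of 60 volunteers, 20 in each group from the following groups", and 3 × 20 = 60 agrees. Section 6 supplies destruction and replacement. The documents give no expected withdrawal rate and no target for (3) or (4), so there is no planned feasibility figure to reproduce.

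**Assumed.** w = withdrawals replaced in a group; x = retained participants, out of 20, who provide; y = withdrawers, out of w, who had provided before leaving.

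**Step 1: formulas.**

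- Retained participants only: x/20.
- Everyone consented: (x + y)/(20 + w).
- Retained minus everyone: (wx − 20y) / [20(20 + w)].

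The retained figure is too high when y/w is below x/20, that is, when leavers provided less often than stayers. It is too low when they provided more often. It is exact when w = 0.

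**Step 2: what can be recovered.** If the withdrawal forms survive and are counted, w is known. If y has been destroyed, the all-consented figure is only bounded, from x/(20 + w) with y = 0 to (x + w)/(20 + w) with y = w. The width of that range is w/(20 + w). If the forms do not survive and no other count is kept, w is unknown too and even these bounds are unavailable.

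**Step 3: numbers over a range of w.**

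| w | x | Retained only | Lowest, all consented | Highest, all consented |
|---|---|---|---|---|
| 0 | 20 | 100% | 100% | 100% |
| 0 | 18 | 90% | 90% | 90% |
| 2 | 20 | 100% | 20/22 = 90.9% | 22/22 = 100% |
| 2 | 18 | 90% | 18/22 = 81.8% | 20/22 = 90.9% |
| 5 | 20 | 100% | 20/25 = 80.0% | 25/25 = 100% |
| 5 | 18 | 90% | 18/25 = 72.0% | 23/25 = 92.0% |
| 10 | 20 | 100% | 20/30 = 66.7% | 30/30 = 100% |
| 10 | 18 | 90% | 18/30 = 60.0% | 28/30 = 93.3% |

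**Step 4: direction and size.** At w = 2 the largest overstatement is 9.1 points (x = 20) or 8.2 points (x = 18). At w = 5 it is 20 or 18 points. The opposite error is smaller: with x = 18 it is at most 0.9 points at w = 2 and 2 points at w = 5. With x = 20 the retained figure cannot be too low. For x = 18 and w = 5 the break-even is y = 4.5, so only if all five leavers had provided would the retained figure understate feasibility.

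**The case against.** The strongest reply is that the protocol never limits (3) and (4) to people who stay. A reader might infer from Section 6 that the proportions are calculated on non-withdrawers and therefore overstate feasibility. The documents do not say so; the denominator is simply undefined. The count may also be recoverable. A withdrawal form is required, Section 7.1 records study group on the CRF, and Section 10.2 has the master file hold the CRFs of everyone recruited. This stands, and it limits the point to a risk. It does not remove the risk, because the protocol does not say that the form or CRF escapes destruction, and a count alone does not show what each leaver provided.

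Other tempting readings also go too far:

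- **That the retained group will always show 20 out of 20.** Someone who cannot give a sample need not withdraw and then stays in as a failure. Section 9.3 expects missing samples.
- **That data are certainly destroyed after distress-related withdrawal.** The words about both cases govern the form. Destruction is stated for a participant who wishes to leave. Extending it to distress is a plausible inference from the sentence on keeping samples, but it is not stated.
- **That leavers' experience is wholly lost.** It is true that "A study completion questionnaire will be introduced after sampling is complete (Appendix B", but Section 3.1 also seeks the views of carers, managers, staff and relatives.
- **That losses will concentrate in the challenging-behaviour group, or that Section 6 is what biases the microbiota comparison.** The documents give no figures for the first. On the second, residents who will not tolerate sampling yield no microbiota data under any withdrawal rule.

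Finally, destruction can be defended as protection for vulnerable people. That also stands, and the fix does not require keeping data or samples by default.

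**Conclusion.** The point holds as a defect in how feasibility will be measured. It does not show that the reported figures will be wrong. A stated rule discards what each withdrawer provided, replacement conceals the gap, and the denominator that could correct for it is undefined. The likely error is optimistic, on the assumption that leavers provided less often than stayers. It is zero without withdrawals, up to about 8 to 9 points at two withdrawals per group and 18 to 20 points at five, taking 18 or 20 of the retained 20 as providing. These withdrawal numbers are assumptions. Under the present rule even the direction could not be established afterwards.

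The reach is limited: two of four descriptive measures under a secondary outcome, with no progression threshold in the documents that depends on them. The reason to act before the first withdrawal is that the loss is permanent.

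**What to change.** **Section 6.** State that the withdrawal form, or a separate non-identifying log, is exempt from destruction. It should record study group, stage reached, number of samples and data items given, who initiated the withdrawal, and the reason where one is offered. Reconcile this with the sentence requiring everything collected to be destroyed, and describe it in the information sheet. State whether destruction also applies to distress-related withdrawals.

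**Section 3.1.** Define (3) and (4) with everyone consented to the group as the denominator. Count withdrawers by what they actually provided, not automatically as failures. Report withdrawals and replacements by group. Replacement may continue for the microbiota comparison, but a replacement adds to the feasibility denominator and does not stand in for the person who left.

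**Cost.** A small protocol and information-sheet amendment, a few extra fields on a form that already exists, and probably less favourable feasibility figures. Destruction of the withdrawer's other data and samples can remain as written.

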7.1. Data Collection

Faecal samples will be analysed for SCFA profile and DNA bacterial profile. Samples will be stored with anonymised labels for up to 10 years. The volunteer phenotype (informing the study group) will be recorded on the CRF. Consent will be sought from subjects to collect faecal samples. Samples from Aberdeen nursing homes will be collected to maintain/ensure sample quality and integrity. These will be collected from the care home by one of the research staff from the Rowett Institute. All food diaries and other questionnaires will be anonymised following recruitment, and stored in a locked filing cabinet in the care home manager's office prior to collection by study researchers. Final storage will be locked filing cabinets in Human Nutrition Unit, or on a secure shared drive, accessible only by the researchers and auditors of the sponsor (for auditing purpose).

7.2. Data Management System

All data subsequently collected will be stored appropriately. Participants' identities are strictly confidential. We will allocate a unique subject code for the individual participants and all the data will be recorded using this code. Only the research team will have access to participants' full details, which will be saved on a shared drive with limited access on password-locked University computers. The hard copy will be stored in locked filing cabinet.

The CI will authorise and maintain adequate and accurate source documents designed to record all observations and other pertinent data for each subject. Data collection will be the responsibility of the CI in this study. Data will be recorded on paper CRFs, which will subsequently be entered onto a secure, password protected study database in SPSS format, by the research team. Electronic database will be held within University computer system in a shared study folder with restricted assessed to study team members and statisticians involved in the study who will be identified in study delegation log. All CRFs and original paper data will be safely stored in locked filing cabinet and researchers will be able to double check the raw data with the electronic file and original file. Database is owned by researchers and the Chief Investigator is the data controller. Data will be entered twice for validation purpose. Data queries will be addressed by the research team members with specific statistical expertise. All University data were stored with a back-up. CRF data will be part of the database. Database may hold additional data collected from the questionnaire surveys; these will be in the form of separate sheets of data which will form complete database.

Subjects will not be identified by name in the study database or on any study documents to be collected, but will be identified by a unique subject number. Source data are contained in source documents (original records). All the source data will be recorded in CRFs or original document form from research team. Data will be transferred into an electronic file and saved in password lock computer. All data will be transferred into an SPSS/Excel files as appropriate by the research nurse. A copy of the CRF will remain at the Investigator's site file at the completion of the study.

Some of the samples will be sent, anonymously, to the bioinformatics team at the University of Aberdeen for final analysis. This means samples will be referred to by the unique study ID number. Any information collected by these third parties will utilise these coded details for all data output. Support provided by Statisticians from biomathematics and Statistics Scotland.

8. Labs and Samples Analysis

Level 5 laboratory at The Rowett Institute, University of Aberdeen will be where the faecal sample analysis will be conducted, under supervision of [name]. The samples will be analysed for short chain fatty acid profile (SCFA) and the bacterial DNA will be extracted for genome analysis. When the study is complete, the faecal samples will be destroyed.

8.1. The faecal/stool samples will be collected by inserting the sample collection container (pre-lined with two plastic bags, the inner one with holes) into the commode when the volunteer needs to defecate. The carer will separate the bags and store the sealed bag containing the faecal sample only in the sealed container and inform the lab that a sample is ready for collection. Samples will be transferred to the Rowett institute (University of Aberdeen) and stored in a -70 +/-5 °C freezer in a glycerol buffer for up to 2 weeks prior to DNA extraction. Extracted DNA will be further stored in a -70 +/-5 °C freezer in the Cat 2 grade lab until all volunteers finish the trial. All the samples will be anonymised. All freezers are calibrated and monitored by research team regularly. Final analysis (by the Bioinformatics team) will be done at the end of the study.

After carrying out necessary tests, the samples will be destroyed as per sponsor's regulations of disposing samples.

9. Statistics and Data Analysis

9.1. Sample Size Calculation

We have examined existing data held at RINH with the statisticians from Biomathematics and Statistics Scotland (BioSS) on gut bacteria in faecal samples. The power calculations indicate that with 20 volunteers on a controlled diet the sample will provide at least 90% power to detect shifts of 20% or more in SCFA and metabolites, and a difference of 45% or more in bacteria between groups. Previous studies have shown that such shifts are achievable in healthy and diseased patient groups.

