Changes in dietary composition and diversity were considered the main drivers of the shifts in gut bacteria profile. In this multi-disciplinary research study, we will investigate the gut microbiota composition in people with Alzheimer's dementia with challenging behaviours, test the feasibility of recruitment, and provide initial data to support a future grant application involving a dietary intervention study in patients with Alzheimer's disease.

We will test our hypothesis that the gut-brain axis promotes behavioural changes in Alzheimer's dementia and is responsive to changes in gut microbiota profile, by comparing the gut microbiota profile between three participant groups (1) Alzheimer's dementia with challenging behaviour, (2) Alzheimer's dementia without challenging behaviour, and (3) a control group of healthy age-matched elderly. We will also carry out a survey to care homes to assess their willingness to participate in dietary supplementation study.

1. Introduction

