9.2. Proposed Analysis

Data will be analysed using SPSS (latest version available at the time of analysis). Data will be presented descriptively and comparisons will be made among 3 groups. Parametric and non-parametric statistical tests will be applied for normally and non-normally distributed data, respectively.

Care home survey data will be analysed using descriptive analysis to estimate the secondary objectives. Textual data will be transcribed verbatim and themes will be derived using thematic analysis.

Questionnaire data will also be transcribed verbatim and summarised based on emerging theme bases on experiences and views of participants (when able to provide consent), carers and family members.

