9.3. Missing Data

The two time points in this study will be used to show consistency of microbial profiles within an individual. If there are missing data points then a reduced dataset of the double time points will be analysed, and an additional analysis of single time points will be made. Having double collection times from each individual will also test the feasibility of the collection process for the main study. We will collect menus from both weeks preceding sample collection in order to have some dietary record in the immediate run-up to sample collection.

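### The 90% power claim in section 9.1 assumes a controlled diet, which this observational study does not impose

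*Combined protocol and SAP*

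**What the plan says.** Section 9.1 (Sample Size Calculation) reports that existing data on gut bacteria in faecal samples were examined with statisticians. It concludes that "with 20 volunteers on a controlled diet the sample will provide at least 90% power to detect shifts of 20% or more". That threshold applies to SCFA and metabolites; for the bacterial measurements the plan gives instead "a difference of 45% or more in bacteria between groups".

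The design is in section 3.1: "An observational case-controlled study with three groups of participants with 1:1:1 will be carried out", with 20 residents per group. On diet, the same section says: "Additional information on regular diet composition will be collected by accessing the weekly care home menu". Section 9.3 adds: "We will collect menus from both weeks preceding sample collection in order to have some dietary record". The study matrix (3.2) lists a food menu at enrolment and no dietary procedure. The eligibility criteria (4.2, 4.3) do not mention diet.

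On analysis, section 9.2 says that "comparisons will be made among 3 groups", using parametric or non-parametric tests according to distribution. Each person gives two faecal samples. Section 9.3 gives their role: "The two time points in this study will be used to show consistency of microbial profiles within an individual".

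**The concern.** The power statement carries an explicit condition, and no part of the protocol meets it. Power depends on the spread between people. An SD taken from volunteers eating a controlled diet may be smaller than the SD among residents of several care homes eating as usual. The protocol itself treats diet as important to the outcome; its opening summary says: "Changes in dietary composition and diversity were considered the main drivers of the shifts in gut bacteria profile". Carrying a controlled-diet SD over to usual diet therefore needs a justification, and none is given.

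Section 2.1.1 makes the three-group comparison the primary objective, and 9.1 is the only support for 20 per group. As written, a reader cannot tell what difference the study could detect. A null result could be misread as evidence against differences of 20% in SCFA or 45% in bacteria. The results are also intended to support a grant application for a larger study, where a realistic SD and detectable difference would matter.

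**Working it through.** **Inputs from section 9.1:** power of at least 90%; 20 volunteers; differences of 20% (SCFA and metabolites) and 45% (bacteria). **From section 3.1:** three groups of 20. **Not stated anywhere:** SD, alpha, sidedness, test, contrast, multiplicity adjustment, or how the two samples per person enter. **Assumed here:** one pairwise comparison of 20 versus 20, two-sided alpha 0.05, t test.

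**Step 1: the plan's own figure.** It cannot be reproduced forwards without an SD, so it is solved backwards. With standardised difference d = δ/SD, the test has 2 × 20 − 2 = 38 degrees of freedom and noncentrality d × √(20/2). Power of 90% requires d = 1.052, so:

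- SCFA: SD = 20/1.052 = 19.0% of the mean
- Bacteria: SD = 45/1.052 = 42.8% of the mean

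The implied SD changes with the unstated choices:

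| Reading of 9.1 | SD for 20% shift | SD for 45% difference |
|---|---|---|
| Two-sample t, two-sided 0.05 | 19.0% | 42.8% |
| Same, normal approximation | 19.5% | 43.9% |
| Normal approximation, one-sided 0.05 | 21.6% | 48.6% |
| Normal approximation, alpha 0.05/3 | 17.2% | 38.7% |
| Three-group F test, one mean midway between the others | 17.3% | 39.0% |

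**Step 2: a larger SD on usual diet.** The increases are assumptions; the documents give no value. Start from exactly 90% power and multiply the SD by k. Then d becomes 1.052/k, and the difference detectable with 90% power becomes k × 20% or k × 45%.

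| k | d | Power | Detectable, SCFA | Detectable, bacteria |
|---|---|---|---|---|
| 1.10 | 0.956 | 84% | 22% | 50% |
| 1.25 | 0.842 | 74% | 25% | 56% |
| 1.50 | 0.701 | 58% | 30% | 68% |

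A simulation of 200,000 runs gave 83.8%, 73.9% and 58.0%.

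**Step 3: slack in the words at least.** The true starting power may exceed 90%.

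- From 95%: d = 1.170, so the SD can rise by 1.170/1.052 − 1 = 11% before power falls below 90%. At +25% and +50%, power is 82% and 67%.
- From 99%: d = 1.391, so the SD can rise by 1.391/1.052 − 1 = 32%. At +25% and +50%, power is 93% and 82%.

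**Step 4: if the source calculation was within-person.** This is not established, and the reference to groups in the same sentence points the other way. A paired test with 20 people has 90% power at a standardised difference of 0.764. The SD of the difference is then 20/0.764 = 26.2%, and the within-person SD is 26.2/√2 = 18.5%. For 20 versus 20, intraclass correlations of 0.3 to 0.7 then give power of 80% down to 45% on one sample per person, and 93% down to 51% on the mean of two.

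**The case against.** The strongest reply is that all participants live in care homes with catered weekly menus, so their diets may be more alike than those of people living independently, and the rise in SD could be small. That possibility stands. It does not turn usual diet into a controlled one: a menu records what is offered, more than one home is approached, and neither menus across homes nor intake within a home is standardised.

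Second, the summary's sentence on diet is in the past tense and concerns shifts in bacterial profile. It says nothing about between-person SD or SCFA. That is fair: the link from diet to the SD is a reasonable inference, not something the documents state.

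Third, the SD increases above have no source, the powers range widely, and all assume a t test although section 9.2 allows non-parametric tests. They show sensitivity and are not evidence that the study is underpowered.

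Fourth, the study is partly a feasibility exercise that leads to a later one. That is true of the opening summary and the secondary outcome. But the primary objective is the group comparison, and 9.1 makes a formal power claim without calling 20 per group a pilot size.

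Finally, the missing alpha, test and contrast are ordinary reporting gaps that would exist even if diet were controlled. They matter here because they prevent a reader from repairing the figure.

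**Conclusion.** The concern holds. The only power statement behind 20 per group rests on a condition that this design does not impose, so the 90% figure is unsupported for this study. No stated number is shown to be miscalculated, and true power is not shown to be below 90%. On the t-test assumptions above, 90% power would still hold if the between-person SD on usual diet were no more than about 19% of the mean for SCFA and 43% for bacteria; the documents do not say whether it is. If the starting power was exactly 90%, SD rises of 10% to 50% would bring it to between 84% and 58%. If the starting power was 99%, rises of 25% and 50% would leave 93% and 82%. The mismatch in the text is certain; the size of any loss is unknown. This should be fixed.

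**What to change.** Recompute section 9.1 from the same existing data, using a between-person SD on habitual diet for 20 versus 20. State that SD, alpha and sidedness, the test, the contrast, any adjustment for three comparisons, and whether the two samples per person are averaged or modelled. Replace the 90%, 20% and 45% figures with the result.

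If no habitual-diet SD is available, remove the 90% claim, describe 20 per group as a pilot size, and tabulate the detectable difference by assumed SD. For 20 versus 20, two-sided 5% and 90% power, the detectable difference is 1.052 × SD:

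| SD (% of mean) | 15 | 20 | 30 | 40 | 50 |
|---|---|---|---|---|---|
| Detectable difference (% of mean) | 16 | 21 | 32 | 42 | 53 |

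The cost is one paragraph or a small table in 9.1. The stated figure may become less favourable. No extra participants or procedures are needed.
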